Study Protocol June 20, 2022 IRB approved 02/14/19

NCT03757819 Transcranial Direct Current Stimulation and Walking in Multiple Sclerosis

A single-blind, sham-controlled, randomized, cross-over design was employed. Subjects attended three experimental sessions. In the first session, participants gave consent, completed the isokinetic strength testing of the knee extensors and flexors to objectively determine the more-affected leg, and self-selected a comfortable walking speed on the treadmill to be used during sessions 2 and 3. At least three days after the first session, Session 2 was completed. Sessions 2 and 3 were separated by at least seven days to allow tDCS effects to dissipate. Prior to sessions 2 and 3, the participants were asked to fast for a minimum of 6 h before FDG administration. At the beginning of sessions 2 and 3, the participants' height and weight were measured, blood glucose levels were determined, and an IV catheter was inserted for FDG injection. Blood glucose level was required to be equal to or less than 200 mg/dL in order to proceed with FDG administration and PET scanning. During sessions 2 and 3, either Sham (0 mA) or tDCS (3 mA) was applied (determined through randomization) to the motor cortex (M1) area corresponding to the more-affected leg for 20 min. The purpose (e.g., enhancing motor learning or improving motor performance) of tDCS may determine stimulation timing. Studies on motor learning often apply tDCS during a task to improve acquisition. In contrast, tDCS was applied before the motor performance of a well-learned task (walking) in the current study. It has previously been demonstrated that tDCS has ambiguous effects on cortical excitability during stimulation, but significantly and consistently increased cortical excitability after stimulation [48]. Moreover, when comparing tDCS before and during a 6-min walk test in PwMS, it was found that stimulation before increased gait velocity, whereas stimulation during resulted in a decrease in the distance walked. Therefore, in this study participants underwent 20 min of tDCS then rested for 10 min to allow for peak stimulation effects before walking on a treadmill for 20 min. Ratings of Perceived Exhaustion (RPE) were collected at the end of each minute during the walking task. Approximately two minutes into treadmill walking, $10 \pm 10\%$ mCi of FDG was administered via IV injection. Immediately after walking was completed, participants were positioned in the PET/computed tomography (CT) scanner and a whole body (top of head to toes) scan was completed to evaluate glucose uptake in the leg muscles.

Data Analysis

Twenty regions of interest (ROIs) were drawn on the CT scan from each experimental session to locate the skeletal muscles of the lower limbs. In the upper leg, the knee extensors (rectus femoris, vastus medialis, vastus intermedius, and vastus lateralis) and knee flexors (long and short head of the biceps femoris, semimembranosus, semitendinosus, sartorius, and gracilis) were identified. In the lower leg, the plantar flexors (gastrocnemius, soleus, peroneus longus, peroneus brevis, flexor digitorum longus, flexor hallucis longus, and tibialis posterior) and the dorsiflexors (tibialis anterior, extensor digitorum longus, and extensor hallucis longus) were identified. The PET images were acquired immediately after the treadmill task and, therefore, the glucose uptake values closely reflected the uptake of FDG during walking. Standardized uptake values (SUV) based on the injected dose and body weight were calculated for each muscle. Although the participants fasted for a minimum of 6 h in order to minimize the impact, SUVs may be affected by blood glucose and insulin levels. Therefore, the SUV data were analyzed without normalization and as values normalized to standard blood glucose (adjusted to 100 mg/dL), and/or the liver as a reference tissue, to allow for comparison across experimental sessions. The data were analyzed using PMOD Version 4.001 (PMD Technologies LLC, Zürich,

Switzerland). The more-affected (weaker) legs were assigned using the knee extensor torque data obtained in Session 1. Asymmetry indices (AIs) were calculated to determine the magnitude of the asymmetry in SUVs between the legs using a previously used equation (Equation (1)). An AI greater than 10% was considered asymmetric.

Statistical Analysis

In order to compare muscle activity between the legs and experimental sessions, SUVs were averaged for each muscle group (knee extensors, knee flexors, plantar flexors, and dorsiflexors). The assumptions for normality were investigated via histograms, Q-Q plots, and the Shapiro-Wilk test, but were not met. Therefore, nonparametric paired tests (Wilcoxon tests) were performed on the normalized data to compare the muscle groups of the left and right leg within each condition (e.g., left vs. right knee extensors during the tDCS condition) and to compare the muscle groups of each leg between conditions (e.g., left knee extensors in Sham vs. tDCS). Significance was accepted at $p < 0.05$. Analyses were performed using GraphPad Prism 8.1.2 (GraphPad Software, San Diego, CA, USA).

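### No listed test asks whether tDCS changed the difference between the legs: the leg-by-condition contrast is missing

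*Combined protocol and SAP*

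**What the plan says.** The opening description of the design sets up a within-person comparison: "A single-blind, sham-controlled, randomized, cross-over design was employed". Active or sham stimulation was applied "to the motor cortex (M1) area corresponding to the more-affected leg for 20 min", so the intervention is directed at one side.

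Under Statistical Analysis, "SUVs were averaged for each muscle group (knee extensors, knee flexors, plantar flexors, and dorsiflexors". Two families of paired Wilcoxon tests follow, each test judged at 0.05:

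- "to compare the muscle groups of the left and right leg within each condition (e.g., left vs. right knee extensors during the tDCS condition"
- "to compare the muscle groups of each leg between conditions (e.g., left knee extensors in Sham vs. tDCS"

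Under Data Analysis, "Asymmetry indices (AIs) were calculated to determine the magnitude of the asymmetry in SUVs between the legs", and "An AI greater than 10% was considered asymmetric". The same section says SUVs were analysed without normalisation and as "values normalized to standard blood glucose (adjusted to 100 mg/dL), and/or the liver as a reference tissue". No section attaches a test to the asymmetry index, and no interaction model is described.

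**The concern.** The plan tests legs within conditions and conditions within legs. It does not test the combination, which is whether the gap between the legs under tDCS differs from the gap under sham. That question arises naturally here, because stimulation is lateralised, the weaker leg is identified in advance by torque testing, and an asymmetry index is computed.

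A reader who wants to compare asymmetry across conditions has only two p-values from the listed tests, one for sham and one for tDCS. Finding one below 0.05 and the other above it is not a test of change. The same holds for one leg significant and the other not in the sham-versus-tDCS family. Any claim that tDCS reduced asymmetry, or acted preferentially on the targeted leg, would have no test behind it.

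**Working it through.** **Count of listed tests.** Four muscle groups × two conditions = 8 left-versus-right tests. Four groups × two legs = 8 sham-versus-tDCS tests. That is 16 per normalisation, of which 0 are leg-by-condition contrasts. The asymmetry index is a description with a cut-off and adds none.

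**What discordant significance is worth.** The documents give no sample size, SD, size of asymmetry, between-session correlation or split of weaker sides, so there is no planned figure to reproduce and every input below is assumed. The simulation used 20,000 replicates per cell and exact two-sided signed-rank tests at 0.05, with **no** tDCS effect on asymmetry. The grid was n = 8, 12, 20; asymmetry 0, 0.2, 0.65, 1.2 SD of the between-leg difference; between-session correlation 0, 0.5, 0.8; weaker side split 100/0, 70/30, 50/50. The table shows how often exactly one of the two within-condition tests is significant:

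| Assumed setting | corr. 0 | corr. 0.5 | corr. 0.8 |
|---|---|---|---|
| n=12, 0.65 SD, all weaker on one side | 50% | 35% | 23% |
| n=12, 0.65 SD, sides 70/30 | 17% | 12% | 9% |
| n=12, 0.65 SD, sides 50/50 | 8% | 7% | 5% |
| n=12, no asymmetry | 8% | 7% | 6% |
| n=20, 1.2 SD, all weaker on one side | 0.3% | 0.2% | 0.2% |

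The first row is the worst case. It can be checked by hand: if the sessions are independent and each test has power p, discordance is 2p(1−p). With p about 0.49, 2 × 0.49 × 0.51 = 0.50, which is the maximum of that expression. By symmetry, half of each entry is significant under sham only. In the 70/30 and 50/50 rows each participant's weaker side is drawn at random; with an exactly fixed split they fall to about 9%/7%/6% and 3%/3%/2%. Across the whole grid, discordance runs from 0.2% to 49.5%, and the direct paired test rejects in 3.7% to 5.2%.

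**The same problem between legs.** If both legs shift equally by 0.65 SD (n=12), exactly one leg is significant in 50%/36%/23% of trials at between-leg correlations of change of 0/0.5/0.8.

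**Effect of normalisation.** Let M and L be the group-mean SUVs of the more- and less-affected leg in one session. Glucose adjustment and liver referencing both multiply M and L by the same session factor c, and log(cM) − log(cL) = log M − log L. The log-ratio contrast is therefore identical under every reading of the and/or normalisation, and with none. The per-leg sham-versus-tDCS tests do not have this property, because c differs between sessions.

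**Power of the direct test.** Let each leg's session-to-session change have variance σ² and between-leg correlation r. The change in the leg difference has variance 2(1−r)σ². This is below σ² only if r > 0.5, so for an effect in one leg the direct test gains on the per-leg test only above that value. With an effect of 0.8σ in the targeted leg only and n=12:

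| Test | r=0 | r=0.25 | r=0.5 | r=0.75 |
|---|---|---|---|---|
| Per-leg, targeted leg, 0.05 | 67% | 67% | 67% | 67% |
| Direct, 0.05 | 39% | 50% | 67% | 92% |
| Direct, 0.0125 (Holm's first step) | 20% | 28% | 43% | 78% |

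**Multiplicity and smallest p.** Four unadjusted tests at 0.05 give 1 − 0.95⁴ = 18.5% family-wise error if independent (bound 4 × 0.05 = 20%). Holm's first step is 0.05/4 = 0.0125. The smallest exact two-sided signed-rank p is 2/2⁷ = 0.0156 at n=7 and 2/2⁸ = 0.0078 at n=8.

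**The case against.** The strongest reply is that the harm is hypothetical. The documents state no primary hypothesis or endpoint and do not name change in asymmetry as a target. The declared purpose is to compare activity across legs and across sessions, and the two test families do that. The sham-versus-tDCS test within each leg is a valid randomised comparison, so an effect on the targeted leg is already tested. No rule in the text treats significance in one condition only as an effect. All of this stands. It is why the point is an addition worth making and not the correction of a wrong test.

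Second, the discordance range is wide and rests on assumptions. The 50% figure needs power near one half, all participants weaker on one side and no correlation between sessions, and the last is hard to credit for the same person at the same treadmill speed. This also stands: 50% is a worst case, and the weaker-side split drives much of the range. The omission itself can be seen in the text and does not depend on the simulation.

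Third, the asymmetry index may have been compared between sessions without this being written down. That is possible, but no such test is stated.

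Fourth, the added test can have low power, and it comes after the data were examined, since the section reports that normality checks failed. Both are true. They are reasons to keep the per-leg tests and to label the contrast honestly. They do not justify inferring a change in asymmetry without any test.

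**Conclusion.** The concern holds and should be fixed. No stated analysis supports a conclusion that tDCS changed between-leg asymmetry or acted more on one leg than the other. If such a conclusion were drawn from which tests reached 0.05, the chance of a misleading discordant pattern with no true change would be between 0.2% and 50% per muscle group over the settings examined, against 4% to 5% for a direct test. Confidence in the omission is high. Where this trial falls in that range cannot be determined without its sample size, variability, between-session correlation and weaker-side split. The per-leg sham-versus-tDCS comparisons are not called into question.

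**What to change.** For each of the four muscle groups, compute every participant's signed log ratio of more- to less-affected leg SUV in each session. Test tDCS minus sham with one paired Wilcoxon test, report the median change with a 95% confidence interval, and apply Holm across the four groups. This orients the legs by affected side, using the torque-based assignment already made under Data Analysis, whereas the listed examples use left and right; the change should be stated.

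Keep the per-leg sham-versus-tDCS tests. The within-condition leg tests and the 10% cut can still describe asymmetry in each condition, but should not be used to infer an effect of tDCS on it. Because the section describes the analysis as already done, label the contrast as added later. If it is not added, state that no inference about change in asymmetry is made.

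The cost is four paired tests on SUVs already computed, the Holm step and a labelling sentence. There are three limits:

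- For an effect in one leg only, the direct test is weaker than the per-leg test unless more than half of the session-to-session change is shared by both legs.
- With fewer than 8 participants the exact test cannot reach 0.0125.
- Holm here covers only the four added tests; multiplicity over the 16 listed tests is a separate matter.
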